- **ROM (participant reported)**: Participants will be asked to obtain photographs of full elbow flexion and extension at 4 months following trial specific instructions. Images will be transferred to YTU and sponsor in order for measurement of ROM to be undertaken by a central reviewer using the procedure described by Meislin et al. [7]. Two independent assessors will perform each measurement three times, an average will be calculated across all measurements (3x measurements per 2x assessors = 6 measurements in total).
- **Re-operations related to the injury or to remove the fixation material**: Data will be collected on the reasons for re-operation e.g. discomfort, stiffness, prominent fixation device, infection, patient choice, surgeon choice.
- **Resource use and work impact**: Costs associated with each type of surgery and related complications, hospital stays, primary care consultations, work impact of both interventions will be collected (economic evaluation will be given in a separate analysis plan).

Scoring of instruments

DASH

Participants will be asked at baseline (pre and post injury) and at 4, 12, 18 and 24-months (for those reaching 24-months within the follow-up period) post-randomisation to complete the DASH questionnaire. The DASH questionnaire comprises of 30 questions measuring symptoms and function. All items are scored on a 5-point scale from 1 (no difficulty/symptoms) to 5 (extreme difficulty/symptoms). The arithmetic mean of at least 27 of the 30 items is transformed by (mean - 1)*25 into the scale from 0 = no symptoms/full function to 100 = maximal symptoms/no function for the DASH total score [3]. At least 27 out of the 30 items must be completed for a score to be calculated, if less than 27 items are completed then a score will not be calculated. If more than one box per item is selected and the boxes are adjacent, then the worst case will be selected, otherwise the item will be treated as missing.

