The primary analysis and the above model including variables associated with outcome and missingness will assume missing outcome data are missing at random (MAR). However, it is possible that participants who failed to complete follow-up questionnaires differed from those who completed follow-up questionnaires (e.g. had poorer recovery and therefore would have scored lower on the DASH if they had completed the follow-up). This would mean the data were missing not at random (MNAR), and would represent a departure from the MAR assumption.

The sensitivity of the primary analysis results to departures from the MAR assumption may be explored using a pattern-mixture model, implemented using the rctmiss Stata command (13, 14) This command currently supports the use of fixed-effect models only, and therefore a linear regression model comparing the primary outcome at 4-months post-randomisation will be used, adjusting for treatment group, age at randomisation, prescribed NSAIDs, previous elbow fractures, diabetes status, smoking status, and drinks alcohol.

The pattern mixture model works by including a sensitivity parameter quantifying the departure from the MAR assumption. For example, if we expected that those who failed to complete the follow-up at 4-months post-randomisation on average would have scored two points lower on the DASH than those who did attend the follow-up, the sensitivity parameter would be equal to 2. The pattern-mixture model can then be used to obtain an estimate of the treatment effect given this level of departure from the MAR assumption. The rctmiss command estimates the treatment effect for varying values of the sensitivity parameter ranging from zero up to any positive value, which allows for the assessment of the impact of varying degrees of departure from the MAR assumption on the treatment effect estimate.

The rctmiss command will be used to produce a graph of the adjusted mean difference in DASH score between treatment groups for varying values of the sensitivity parameter. This will be done assuming the value of the sensitivity parameter is equal in both groups (missing data are equally informative in both groups), and also assuming the sensitivity parameter is equal to zero in the control group and varying in the intervention group, and vice versa (missing data are only informative in one group and not the other).

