15.1 Accepting non-inferiority

Section x outlines how we will determine whether tension suture repair is non-inferior to tension band wiring. The primary endpoint is the DASH score at 4 months. For treatment to be effective we are looking for a reduction in DASH scores (lower DASH scores are more favourable). When modelling the treatment effect, the treatment allocations will be coded as 1= intervention (tension suture repair) and 0= control (tension band wiring). Therefore a positive effective will mean the treatment difference will be negative. The non-inferiority margin has been specified as 10 and non-inferiority will be accepted if the upper bound of the of the one-sided 97.5% confidence interval for the treatment difference at 4 months lies below the non-inferiority margin of 10 points. Figure 1 shows how we will interpret different possible results.

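### SAP section 11.6 states the DASH direction backwards, so the two one-arm missing-not-at-random curves are in effect swapped if the text is followed literally

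*SAP*

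**What the plan says.** Section 6.2 (scoring of the DASH) sets the scale as "0 = no symptoms/full function to 100 = maximal symptoms/no function". Section 15.1 agrees that "lower DASH scores are more favourable". It codes suture as 1 and wire as 0, so a positive difference is unfavourable to suture, and non-inferiority requires the upper limit to lie below 10.

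Section 11.6 (missing data) allows a pattern-mixture model, run with the Stata command rctmiss, to explore departures from missing at random (MAR). Its rationale is that non-responders may differ, for example because they "had poorer recovery and therefore would have scored lower on the DASH if they had completed the follow-up". The worked example fixes the sign: if non-responders "would have scored two points lower on the DASH than those who did attend the follow-up, the sensitivity parameter would be equal to 2". The command is then described as covering "varying values of the sensitivity parameter ranging from zero up to any positive value". Three scenarios are to be graphed: one "assuming the value of the sensitivity parameter is equal in both groups", one with a departure in the intervention arm only, and one with a departure in the control arm only.

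**The concern.** On a scale where 100 is the worst state, poorer recovery means a higher score. Section 11.6 says the reverse in its rationale and again in the example that defines the parameter, so this is more than one slipped word. With the range described only from zero upward, the definition gives missing participants scores equal to or better than MAR implies, never worse. Poorer recovery is the only mechanism the section offers.

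The direction matters because this is a non-inferiority comparison. An obvious threat to a conclusion of non-inferiority is that suture participants who did not respond had done badly, which would push the upper limit towards 10. The suture-only curve is the natural place to look for that, and under the written definition it moves the other way. The primary model and its repeat with predictors of non-response both assume MAR, so the pattern-mixture model is the only planned analysis of missing data that goes beyond MAR.

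**Working it through.** **Inputs from the SAP.** Margin 10, SD 23, 90% power, one-sided 97.5% limit, 224 evaluable, 20% attrition, total 280 (section 8); 1:1 allocation (section 9); DASH direction (sections 6.2 and 15.1); parameter example of 2 points (section 11.6).

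**Assumptions not in the SAP.** Departures other than 2 points; attrition of 20% in each arm; the 25%/15% split; a MAR estimate of 3.0; a half-width held at its planning value without covariate adjustment.

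**Step 1: the plan's own figure.** n per arm = 2 x (23/10)^2 x (1.960 + 1.282)^2 = 111.2, rounded up to 112. That gives 224 in total, and 224/0.8 = 280. Both figures reproduce, and neither depends on this point.

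**Step 2: scale direction.** Score = (mean item - 1) x 25. A mean item of 1 gives 0 and a mean item of 5 gives 100. Worse function is a higher score, as section 15.1 also says.

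**Step 3: effect on the difference.** Let p be the fraction missing in an arm and d the non-responder mean minus the responder mean on the DASH. Then

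shift in (suture - wire) = p_suture x d_suture - p_wire x d_wire.

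For a parameter of size k, the written definition gives d = -k and the corrected one d = +k. With 20% missing in each arm:

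| k (points) | Suture only, as written | Suture only, corrected | Wire only, as written | Wire only, corrected | Equal in both |
|---|---|---|---|---|---|
| 2 (SAP example) | -0.4 | +0.4 | +0.4 | -0.4 | 0 |
| 5 (assumed) | -1.0 | +1.0 | +1.0 | -1.0 | 0 |
| 10 (assumed) | -2.0 | +2.0 | +2.0 | -2.0 | 0 |

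The two one-arm curves change places. At 10% missing per arm every shift halves.

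**Step 4: unequal missingness, k = 10.** With 25% missing on suture and 15% on wire:

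- As written: suture only -2.5, wire only +1.5, equal in both -1.0.
- Corrected: suture only +2.5, wire only -1.5, equal in both +1.0.

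The largest adverse shift is +1.5 as written against +2.5 corrected, and the equal-in-both curve changes sign. If the split is reversed (15% suture, 25% wire), the largest adverse shift is +2.5 as written against +1.5 corrected. The written version can therefore understate or overstate the adverse case.

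**Step 5: what a reader would see.** SE = 23 x sqrt(2/112) = 3.07; half-width = 1.96 x 3.07 = 6.02. With an assumed MAR estimate of 3.0 the upper limit is 9.02. At k = 10 and 20% missing per arm:

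- Suture only: 9.02 - 2.0 = 7.02 as written; 9.02 + 2.0 = 11.02 corrected.
- Wire only, as written: 9.02 + 2.0 = 11.02.

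The corrected suture-only curve would cross 10 at k = (10 - 6.02 - 3.0)/0.20 = 4.9 points. As written, the same crossing appears on the wire-only curve.

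**The case against.** A reader might infer that the whole analysis flatters suture. The documents do not support that. Of the three planned curves only the suture-only one does so regardless of how missingness falls. The wire-only curve, with the same reversed sign, moves towards the margin, and the equal-in-both curve does not move when missingness is balanced. With equal missingness someone who looks at all three would still see any fragility, though attributed to the wrong arm and mechanism. This objection stands, subject to Step 4.

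A reader might also infer that the analysis will be run the wrong way. The SAP shows no code or command options. If a positive value is simply added to the DASH, missing participants become worse, the curves run correctly, and only the prose is wrong. This stands too: the contradiction in the text is certain, its effect on the run is not.

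The two faulty statements are offered as examples, and the zero-upward range describes what the command can do rather than a chosen sweep. That is fair, but the example is the only definition of the parameter's sign, and the section gives no other range.

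The effect is small on the SAP's own terms: 0.4 points either way for the 2-point example, a difference of 0.8 between the signs, or 8% of the margin. Section 11.6 also expects little missing data. Larger figures rest on an assumed departure. Finally, the analysis is optional, and the SAP itself says it is not directly comparable with the primary model.

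**Conclusion.** The point holds as an internal contradiction that should be fixed. Section 11.6 equates poorer recovery with a lower DASH, while sections 6.2 and 15.1 make lower better. Read literally, no scenario worsens missing participants relative to MAR, and the two one-arm curves are in effect interchanged.

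At 20% missing per arm the suture-only shift is -0.4 instead of +0.4 for the SAP's 2-point example, and -2.0 instead of +2.0 for an assumed 10 points. The numerical span of the three curves is unchanged with equal missingness and differs with unequal missingness.

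It would go too far to conclude that the non-inferiority decision is compromised. That decision rests on the primary model, for which section 15.1 states the direction correctly. The sample size, primary estimate and decision rule are untouched. What is at risk is a supportive graph that is mislabelled, or run with the wrong sign, and then read as reassurance about the suture arm.

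**What to change.** In section 11.6:

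- State that non-responders with poorer recovery would be expected to have a higher DASH, and reword the 2-point example to match.
- Define the sensitivity parameter as mean(missing) minus mean(observed) on the DASH, so that positive is worse.
- Check that the sign passed to rctmiss agrees with that definition, and label the graph axis accordingly.
- Keep the equal, suture-only and wire-only scenarios.

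Optionally, report the suture-only value at which the upper limit reaches 10. That is a useful addition, not part of repairing the contradiction.

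The cost is two text edits, an entry in the SAP amendment log and a sign check in the code. No further data are needed.

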11.5 Primary analysis

DASH scores will be analysed using a mixed-effects regression model, with DASH scores at 4, 12 and 18-months follow-up as the dependent variable, adjusting for baseline DASH scores (pre-injury), age at randomisation (continuous), prescribed NSAIDs (binary; prescribed NSAIDs or not prescribed NSAID), previous elbow fractures (binary; previous elbow fracture or no previous elbow fracture), diabetes status (binary; diabetic or non-diabetic), smoking status (binary; current regular smoker or not a current regular smoker), drinks alcohol (binary; drinks alcohol or does not drink alcohol), randomised treatment group, time, and treatment group-by-time interaction as fixed effects and including treating centre and participant as random effects.

The DASH measure will be taken twice at baseline; pre and post-injury. We have outlined that the preinjury measure will be used in the primary analysis model as pre-injury function is more relevant. The post-injury scores will be examined for balance and if there is an imbalance across arms this will also be added to our primary analysis model.

The correlation of observations within participants over time will be modelled using participant as a random effect. The Akaike information criterion (AIC) will be used to compare models specifying different correlation structures (smaller values preferred), the most appropriate pattern will be used for the final model. All model assumptions will be checked, and if they are in doubt transformations of the outcome data will be considered. The estimated treatment group differences at 4 months will be reported as the primary endpoint with its associated one-sided 97.5% confidence interval. Example tables are provided in the appendix (Section 15.2.2).

Non-inferiority will be accepted if the upper bound of the one-sided 97.5% confidence interval (equivalent to the upper two-sided 95% confidence limit) for the treatment difference at 4 months lies below the non-inferiority margin of 10 points. Further details on this decision can be found in appendix 15.1.

Primary analysis will be checked by a second statistician on completion, this will be documented using *F16: Primary Analysis Sign Off* Form.

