11.6 Sensitivity analyses

Intervention adherence

A Complier Average Causal Effect (CACE) analysis to assess the impact of compliance on treatment estimates will be undertaken for the primary outcome (DASH score at 4-months). Compliance will be based on whether the participant received allocated treatment and also using surgeon self-report forms and image analysis of intra-operative images for fidelity. A two-stage IV regression approach will be used with mixed-effects regression to reflect the primary analysis. This model will be fit using the ivregress stata command. The primary analysis model will be repeated but the variable for randomised treatment group will be replaced with the variable for compliance. The option vce (cluster) will be used to account for repeated measures.

Missing data

We anticipate that missing data for the statistical analysis will be relatively small. The primary outcome will be collected at the 4-months clinic visit which is a routine visit. In the event participants cannot attend in person, procedures are in place to collect the data remotely.

The amount of missing data will be mitigated by including all data in the primary analysis model, which allows the inclusion of any patient with complete baseline data and valid outcome data at one or more follow-up points.

The amount of missing data will be reported for each randomised arm, and we will also compare the baseline characteristics of participants who are included in the primary analysis to ensure that any attrition has not produced any imbalance in the groups in important covariates. To account for any possible bias, a logistic regression will be run to predict non-response (no questionnaires received post-randomisation) including variables collected prior to randomisation. The primary analysis will then be repeated including as covariates all variables found to be significantly predictive of non-response to determine if this affects the parameter estimates.

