While the results of this sensitivity analysis will not be directly comparable to the primary analysis model, it will be able to give an indication of how sensitive the estimate of the treatment effect is to departures from the MAR assumption in the primary outcome data.

In addition to the above analysis, patterns of missingness amongst participants will be summarised descriptively.

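### The missing-not-at-random analysis starts from a 4-month-only regression and not from the primary model, so it cannot locate the departure at which the primary non-inferiority conclusion would fail

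*SAP*

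**What the plan says.** SAP section 11.5 fits one mixed-effects model "with DASH scores at 4, 12 and 18-months follow-up as the dependent variable", with participant and centre as random effects and pre-injury DASH among the covariates. Of its results, "The estimated treatment group differences at 4 months will be reported as the primary endpoint". Section 11.6 says that this approach limits the loss from missing data, because it is one "which allows the inclusion of any patient with complete baseline data and valid outcome data at one or more follow-up points". It states that the primary model assumes missing at random (MAR).

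For departures from MAR, section 11.6 offers a pattern-mixture model through the Stata command rctmiss. The reason for a simpler outcome model is given: "This command currently supports the use of fixed-effect models only". The result is that "a linear regression model comparing the primary outcome at 4-months post-randomisation will be used", with treatment group, age, NSAIDs, previous elbow fracture, diabetes, smoking and alcohol as covariates. Later DASH, pre-injury DASH and centre are not in it. The departure is varied equally in both arms, in the intervention arm alone and in the control arm alone. The section concedes that "the results of this sensitivity analysis will not be directly comparable to the primary analysis model" and describes the output as a guide to sensitivity.

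**The concern.** A departure plot is read from its starting point: beginning at the MAR result, how informative must the missing scores be before the conclusion changes? Here the starting point belongs to another model. Participants who missed 4 months but answered at 12 or 18 months have observed outcomes that carry information on their 4-month state. The primary model uses that information and the MNAR regression discards it. A difference between the plotted curve and the primary result may therefore reflect the discarded visits as well as the departure under study.

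Non-inferiority turns on one limit against one number, 10 points, so the natural question is what departure would bring that limit to 10. The planned graph answers it for a different estimate. The other missing-data analysis in section 11.6 does not fill the gap. It also assumes MAR, and it models non-response as the return of no questionnaire at all, so it passes over people missing only at 4 months.

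**Working it through.** **The plan's own figures.** Section 8 gives SD 23, margin 10, 90% power, a one-sided 97.5% limit and 20% attrition at 4 months. Per arm, n = 2 × 23² × (1.960 + 1.282)² / 10² = 2 × 529 × 10.51 / 100 = 111.2, rounded up to 112. The total is 224, and 224 / 0.80 = 280. Both match the SAP, and nothing below changes them.

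**Who informs which estimate.**

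| DASH record | Primary model | MNAR regression |
|---|---|---|
| 4-month score present | used | used |
| 4-month missing, 12- or 18-month present | used, through within-person correlation | treated as missing; later scores ignored |
| no follow-up score | not used | treated as missing |

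The two analyses part company in the second row.

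**What the planned analysis does show.** With a share p missing at 4 months, a departure d in one arm moves the difference by p × d. At p = 0.20, departures of 2, 5, 10 and 20 points move it by 0.4, 1.0, 2.0 and 4.0.

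**Gap between the two starting points.** This needs values that the documents do not give. Assumed: 140 per arm, true difference 0, DASH SDs 23/20/20 at the three visits, within-person correlation 0.7, about 20% missing at 4 months, and 25% to 75% of those returning later. Suture-arm missingness rises with 12-month DASH (log odds 0.7 per SD). Over 1,500 simulated trials per setting, the 4-month-only mean difference (without covariates) and a likelihood estimate from all three visits were as follows.

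| Return later | 4-month only | All visits | Gap | Closed form |
|---|---|---|---|---|
| 25% | -2.13 | -1.49 | 0.64 | 10.5 × 0.05/0.85 = 0.62 |
| 50% | -2.26 | -1.04 | 1.22 | 10.5 × 0.10/0.90 = 1.17 |
| 75% | -2.18 | -0.46 | 1.72 | 10.5 × 0.15/0.95 = 1.66 |

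The closed form is D × rp / (1 - p + rp), where r is the share returning and D is how much worse the missing suture patients are than the observed ones. In this setting D is about 10.5 points, so the 4-month-only bias should be -0.20 × 10.5 = -2.1, as simulated. Negative values favour suture.

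- *Milder dependence.* At log odds 0.3 the 4-month-only bias is about -1.0, so D is about 1.0 / 0.20 = 5. The closed form gives 5 × 0.05/0.85 = 0.29 to 5 × 0.15/0.95 = 0.79; simulation gave about 0.2 to 0.7.
- *Overall range.* Across 10-20% missing and log odds 0.3 to 0.7, the mean gap is about 0.2 to 1.8. The mildest corner (10% missing, D = 5, 25% returning) is slightly lower by the closed form: 5 × 0.025/0.925 = 0.14.
- *Random missingness.* Both estimates are unbiased. At 20% missing, the SD of their difference was 0.56, 0.74 and 0.95 for 25%, 50% and 75% returning. Over 10-20% missing it is about 0.4 to 1.0.
- *Stronger assumptions.* With correlations 0.5 to 0.85, log odds 0.5 to 1.0 and one later DASH, gaps ran from about 0.35 to 3.2.

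**Effect on the tipping point (illustration, standard error held fixed).** With 112 per arm, SE = 23 × √(2/112) = 3.07 and 1.96 × 3.07 = 6.02. From an estimate of 0, the upper limit reaches 10 at a one-arm departure of (10 - 6.02) / 0.20 = 19.9. From -1 it does so at (10 - 5.02) / 0.20 = 24.9. At 20% missing, each point of gap moves the tipping departure by 1 / 0.20 = 5 points, so 0.2 to 1.8 moves it by 1 to 9. The SAP's own example of a departure is 2.

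**The case against.** The strongest reply is that the endpoint is the 4-month difference, and a participant without a 4-month DASH really is missing it. Shifting missing 4-month scores, in both arms and in each arm alone, is a valid MNAR analysis of that quantity. In the simulated scenario at log odds 0.7, a departure of about 10.5 points towards worse scores in the intervention arm cancels the bias (0.20 × 10.5 = 2.1), and the plan already includes an intervention-only line. At 20% missing, moving the estimate by the full 10 points would take a one-arm departure of 10 / 0.20 = 50. All of this stands. A reader might infer that the planned analysis says nothing about robustness; the documents do not support that.

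A reader might also infer that the primary result is biased or the non-inferiority decision unsafe. No changed decision has been shown. The gaps depend on assumed missingness, and section 11.6 expects little missing data with remote collection available, although section 8 allows for 20%.

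The SAP also discloses the limitation and its cause. That is to its credit, but disclosure does not give the primary model a check of its own, and the cause is a limit of one command and not of the method.

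Finally, the alternative changes what the departure means. Under the plan it is a difference from those who attended; under imputation from later visits it is a residual difference given later DASH, which is harder to elicit. That is a real cost.

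**Conclusion.** The point holds as one of alignment. The only MNAR analysis starts from a model that discards observed 12- and 18-month outcomes used by the primary analysis. It gives a usable indication of how a 4-month-only estimate responds to informative missingness, but it does not give the departure at which the primary model's upper limit reaches 10.

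The size is modest against a 10-point margin, but not against the departures likely to be plotted. It rests on a correlation of 0.7, 10-20% missing at 4 months, 25-75% of those returning later and, for the systematic gap, suture-arm missingness linked to later DASH. The documents give neither that link nor the share returning, so the figures are a range and not a forecast. Adding pre-injury DASH to the regression would be sensible but would not restore the discarded outcomes. This is a worthwhile, inexpensive improvement and not a fault that undermines the trial.

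**What to change.** Replace or supplement the rctmiss regression in section 11.6 with delta-adjusted multiple imputation:

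1. Impute missing DASH separately by arm, from a model holding 4-, 12- and 18-month DASH and all primary-model covariates, including pre-injury DASH.
2. Shift the imputed 4-month values towards worse (higher) scores under the three scenarios already planned. State the direction explicitly, because section 11.6 describes poorer recovery as a lower DASH while the scoring text and appendix 15.1 make higher scores worse.
3. Refit the primary mixed model to each completed dataset and combine by Rubin's rules. The zero-departure point then targets the same quantity as the primary analysis, under a closely matching assumption.
4. Report the departure at which the upper 97.5% limit reaches 10, and tabulate by arm how many participants lack a 4-month score but have a later one.

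The cost is SAP wording, modest extra programming and computing in the same software, and an imputation model fixed in advance. The departure must then be interpreted as conditional on observed later DASH. Sample size, error rate and power are unaffected.

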Randomisation will be undertaken by York Trials Unit (YTU). When patients have given written informed consent and all the baseline forms have been completed, the authorised site research staff will contact YTU either by accessing a secure, internet-based randomisation service website hosted by York Trials Unit (https://ytu.york.ac.uk/YorkRand/) to obtain the patient's treatment allocation and enrol the patient into the study. Research staff will be required to provide the patient's trial identification number and other details to confirm patient eligibility in order to avoid inappropriate entry of patients into the trial. Participants will be randomly allocated in a 1:1 ratio to either tension suture repair or tension band wiring, using computer generated permuted blocks of random sizes, stratified by centre.

The Statistician will not be blinded to group allocation, nor will other members of the study team who are actively involved in the administration of the study. Participants will not be informed of which treatment they have received and the surgical wound is the same. However, if the wire protrudes or becomes uncomfortable, or the participant has sight of the x-ray, it may become apparent to the participant which intervention they have received. The investigator will record on the 4-month follow-up CRF whether they are aware of any inadvertent un-blinding of the participant (without asking the participant).

10. Analysis of internal pilot phase

There will be a 9-month internal pilot phase to assess assumptions about recruitment and the fidelity of implementing the tension suture repair technique.

The recruitment rate (defined as the proportion of eligible patients recruited) and 95% confidence interval (CI) will be estimated from the data collected up to the end of the pilot phase.

A CONSORT diagram will be produced to show the flow of participants through the study and the following outcomes calculated: number of eligible patients; proportion of eligible patients approached for consent; proportion of eligible patients not approached and reasons why; proportion of patients approached who provide consent; proportion of patients approached who do not provide consent; proportion of patients providing consent who are randomised; proportion of patients randomised who do not receive the randomly allocated treatment; proportion of patients dropping out between randomisation and follow-up.

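### The optional pattern-mixture regression leaves out pre-injury DASH and centre, although its stated software limit excludes neither, so its MAR starting point conditions on less than the primary analysis does

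*SAP*

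**What the plan says.** The primary model in SAP Section 11.5 is a mixed-effects regression "with DASH scores at 4, 12 and 18-months follow-up as the dependent variable". It begins its covariate list by "adjusting for baseline DASH scores (pre-injury" version), then adds age, NSAID prescription, previous elbow fracture, diabetes, smoking and alcohol, all as fixed effects, "including treating centre and participant as random effects". The section justifies the pre-injury score as the more relevant of the two baseline measures, and brings in the post-injury score as well if the arms turn out imbalanced on it.

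Section 11.6 (Missing data) says that departures from MAR may be explored with a pattern-mixture model fitted by the Stata command rctmiss. It explains the simpler model as follows: "This command currently supports the use of fixed-effect models only". The replacement is a linear regression of 4-month DASH, "adjusting for treatment group, age at randomisation, prescribed NSAIDs, previous elbow fractures, diabetes status, smoking status, and drinks alcohol". The sensitivity parameter runs upward from zero, the MAR point. The section then warns that "the results of this sensitivity analysis will not be directly comparable to the primary analysis model".

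Section 9 states that allocation was made "using computer generated permuted blocks of random sizes, stratified by centre".

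**The concern.** The pattern-mixture list repeats every baseline covariate of the primary model except pre-injury DASH, and centre is missing too. A restriction to fixed effects accounts for losing the random effects and, with them, the repeated-measures structure. It does not account for losing a covariate that is already a fixed effect, and it does not prevent centre from entering as indicator terms. The SAP gives no other reason.

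The analysis exists to show how the primary result responds when MAR is relaxed. Its zero-departure point should therefore be as close to the primary MAR analysis as the command permits. As written, MAR at that point is conditional on less: pre-injury function and centre are ignored. If non-response is related to pre-injury function differently in the two arms, the starting point can be biased where the primary model is not. Even without such bias, the estimate is less precise if pre-injury DASH predicts 4-month DASH.

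**Working it through.** **1. The two models side by side**

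| Element | Primary model (11.5) | Pattern-mixture regression (11.6) | Explained by the fixed-effects limit? |
|---|---|---|---|
| Outcome data | 4, 12 and 18 months | 4 months only | Yes |
| Participant | random effect | none | Yes |
| Age, NSAIDs, previous fracture, diabetes, smoking, alcohol | fixed | fixed | no change |
| Pre-injury DASH | fixed | absent | No |
| Centre | random effect | absent | Only as a random effect; indicators remain possible |

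**2. The plan's own figure.** Inputs from Section 8: margin 10, SD 23, one-sided alpha 0.025, power 90%, attrition 20%. With a true difference of 0, n per arm = 2 × (1.960 + 1.282)² × 23² / 10² = 111.2, rounded up to 112. The total is 224, and 224 / 0.8 = 280. Both match the SAP, and nothing in this point changes them.

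**3. Precision.** The unadjusted SE at 112 per arm is 23 × √(2/112) = 3.07, so the 95% half-width is 1.96 × 3.07 = 6.02. Adjusting for a covariate with correlation r to the outcome multiplies the SE by √(1 − r²). The upper limit then narrows by 6.02 × (1 − √(1 − r²)):

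- r = 0.2: 6.02 × 0.0202 = 0.12 points
- r = 0.3: 6.02 × 0.0461 = 0.28 points
- r = 0.5: 6.02 × 0.1340 = 0.81 points

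The SAP does not give r. The value that matters is the partial correlation given the other covariates, and it may be small if pre-injury scores cluster near zero.

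**4. Distance from the primary estimate.** A simulation used assumed settings: 280 participants, 20 centres, intraclass correlation 0.02, about 20% missing at 4 months with half of those seen later, within-participant residual correlation 0.6, and 300 trials per setting. The table gives the root-mean-square gap, in DASH points, between the zero-departure estimate and a repeated-measures estimate.

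| r | As written | Plus pre-injury DASH | Plus pre-injury DASH and centre indicators |
|---|---|---|---|
| 0.1 | 1.07 | 1.02 | 0.88 |
| 0.3 | 1.40 | 1.05 | 0.89 |
| 0.5 | 1.78 | 1.02 | 0.78 |

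The gap shrinks but does not close. The remainder reflects the later visits used by the repeated-measures model. The comparator fitted centre as fixed, which probably flatters the last column. Adding 19 centre indicators also raised the SD of the estimate, from 2.83 to 2.98, 2.69 to 2.84 and 2.39 to 2.42. Allocation in the simulation was not stratified, so that cost is probably overstated.

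**5. Conditioning.** In a deliberately adverse case, missingness depended on pre-injury DASH in opposite directions by arm (log-odds 0.7 per SD, true difference 0). The mean zero-departure estimate was −1.75 (r = 0.3) or −3.00 (r = 0.5) as written, 0.14 or 0.10 with pre-injury DASH added, and 0.17 or 0.09 for the repeated-measures model. The sign follows from the assumed direction. This shows that the two MAR assumptions differ; it does not predict a bias in this trial.

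**The case against.** The strongest reply is that the mismatch is disclosed and of limited consequence. Section 11.6 says the results are not directly comparable with the primary model, claims only an indication of sensitivity, and makes the analysis optional. Non-inferiority is judged on the Section 11.5 model alone, which contains both terms. All points on the sensitivity curve come from one regression, so movement away from zero reflects the departure parameter and not the missing covariates. MAR given baseline variables is also examined elsewhere in Section 11.6, where the primary model is refitted with predictors of non-response, and the SAP expects little missing data. Finally, the number and size of centres are not stated, so whether centre indicators are affordable cannot be judged from the document.

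All of this stands, and it limits how serious the point is. It does not remove it: a caveat about comparability is not a reason for leaving out a collected baseline score that the command can take, and the reader is not told that this was done.

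A reader might infer that the two omitted terms are the whole cause of the mismatch, and that restoring them would make the curve start at the primary estimate. The documents do not support that. The primary model also uses 12- and 18-month scores, and includes participants who have no 4-month score.

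**Conclusion.** The pattern-mixture regression omits pre-injury DASH for no reason that the SAP gives, and the software limit it cites does not supply one. The same holds in principle for centre, but there the practical case depends on centre numbers and sizes that the SAP does not report. The zero-departure point therefore conditions on less information than the primary analysis. This is the avoidable part of a disclosed mismatch; the part due to 4-month data alone would remain.

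The size is modest: about 0.1, 0.3 or 0.8 points on the upper limit for assumed correlations of 0.2, 0.3 or 0.5, against a margin of 10. A reader might instead inflate 3.07 by 1/√(1 − r²), which gives 0.93 points at r = 0.5. That is not right, because 3.07 comes from the unadjusted SD and so already excludes any gain from pre-injury DASH.

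A reader might also infer that the trial's conclusion is at risk. It is not: the primary non-inferiority decision does not use this regression, and the wider interval from the omission is, taken alone, conservative for non-inferiority. What is affected is how cleanly the sensitivity analysis can be read. It is worth correcting because the correction is nearly free.

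**What to change.** In the Missing data part of Section 11.6:

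- Add pre-injury DASH to the covariate list of the pattern-mixture regression, and post-injury DASH as well if the imbalance rule in Section 11.5 brings it into the primary model.
- Add centre as fixed indicator terms where centre sizes allow, with a rule written in advance for pooling very small centres.
- Report the zero-departure estimate and its upper limit beside the primary estimate, and state that an exact match is not expected because the primary model also uses the later visits.

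The cost is a change of SAP wording and a longer covariate list in the command. No new data are needed and the sample size stays at 224 evaluable and 280 randomised. Pre-injury DASH uses one degree of freedom. Centre uses one fewer than the number of centres or pooled groups, so if many centres are small, pre-injury DASH alone secures the main part of the improvement.
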